### **Statistical analyses**

Data processing was performed using R (Version 3.3.3) and RStudio (Version 1.1.453). Statistical analyses were performed using SigmaPlot 14 (Systat Software Inc., San Jose, CA). Data were tested for normality and parametric or non-parametric assumptions were used as appropriate. Comparisons of cardiovascular outcomes and symptoms between conditions (lidocaine and placebo) and test phases (baseline and during bowel care) were performed using two-way repeated measures ANOVA. Spearman rank correlations and

linear regressions were used to assess relationships between variables. Fisher's exact test was used to evaluate differences in proportions of responses between test conditions. Student t tests were used to compare responses between placebo and lidocaine conditions (e.g. time to complete bowel care). Statistical significance was assumed at  $p<0.05$ . Where appropriate, data are represented as mean  $\pm$  standard error, unless otherwise stated. Researchers, participants, care providers, and those analysing the data were blinded to the test condition. Researchers were unblinded just prior to statistical analyses.

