### Participants

Participants were recruited using a multi-method approach. Print advertisements were circulated through our community partner, Spinal Cord Injury British Columbia, via their quarterly publication, *The Spin*, and online advertisements were posted through our institutional website ([www.icord.org](http://www.icord.org)).

Eligible participants were individuals aged >18 years of age with chronic (>1 year) traumatic high level (T6 or above) SCI, who had an established bowel care routine, and a prior history of AD. Individuals were excluded if they had a medical/psychiatric condition or substance abuse disorder, used a ventilator, had a colostomy, or did not perform regular bowel care for any reason. Additional exclusion criteria included skin breakdown in the areas receiving pressure during the bowel program, inability to communicate in English, use of medicines containing lidocaine, allergy to lidocaine, and pregnancy.

Our primary outcome measure was the difference in systolic arterial pressure between the placebo and lidocaine conditions. We determined a meaningful difference to detect in blood pressure between the two study arms of 10mmHg (based on previous unpublished observations from our lab). With a power of 0.8 and alpha of 0.05, we determined a sample size of 13 individuals would be necessary to ensure statistical confidence in our ability to detect differences in this primary outcome measure.

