### Experimental Procedure

We conducted a registered double-blind placebo-controlled crossover clinical trial where participants were randomised to a series of two treatments: lidocaine lubricant (Xylocaine 2%) and standard lubricant (KY Jelly; placebo) on two consecutive at-home visits (**Figure 1**). The sequence of conditions was determined by random draw, using a complete randomised design, by a researcher external to the research team; seven participants were randomised to the lidocaine arm of the study first, and six to the placebo arm of the study first. Testing took place between August 2016 and October 2018.

Prior to the first visit, participants completed a questionnaire about their bowel management and general bowel continence [5]. On each visit, participants were fitted with a standard three-lead electrocardiogram (ECG; lead II) and a non-invasive beat-to-beat finger blood pressure monitor (Finometer Midi, Finapres Medical Systems [FMS], Amsterdam, Netherlands). After a 10-minute baseline recording (sampling rate 200Hz) participants inserted 5mL of lubricant into the rectum using a specialised device (Lube Launcher XL, CleanStream, Huntington Beach, USA) to ensure that a minimum amount of lubricant was administered. Following insertion of the lubricant, participants waited 5-min before starting bowel care (to allow for mucosal absorption of lidocaine, which has a typical onset of action of 3-5 minutes). Participants were then provided with an additional 15mL of lubricant and asked to perform their bowel care routine as

usual, replacing their normal lubricant with the lubricant provided for that day. The maximum recommended dosage of lidocaine is 600mg/12 hour. The dosage provided (20ml of 2% lidocaine) is equivalent to 400mg. The 20ml volume was determined based on discussion with bowel care providers and individuals with SCI concerning their typical lubricant needs. This dosing strategy is in line with other similar studies. Given the typical half-life of lidocaine (1.5-2 hours) we are confident there was optimal dosing throughout the duration of bowel care.

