Five minutes after insertion of the test lubricant, a timer was started and the participant commenced their usual care routine. Bowel care routines were not standardised because the primary interest was to investigate the real-world feasibility and impact of this clinical recommendation in a community setting with usual participant care routines. When the participant signalled the end of their care routine (defined as the time when bowel evacuation was completed, prior to cleaning), the timer was stopped, and the bowel care duration noted. The cardiovascular monitoring equipment was then removed. Participants then completed a questionnaire specific to their bowel care on that day, reporting the method of bowel care employed as well as the severity of cardiovascular symptoms experienced [5]. Self-reported symptoms of AD were determined as described previously [5]. Two participants chose not to complete the post-bowel care questionnaire.

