### **Data analyses**

Beat-to-beat systolic (SAP) and diastolic (DAP) arterial pressures were extracted throughout the testing period. Mean arterial pressure (MAP) was calculated as  $\text{DAP} + 1/3 \times (\text{SAP}-\text{DAP})$ . Heart rate was determined from the R-R interval of the ECG. Stroke volume (SV) and cardiac output (Q) were determined using Modelflow [27,28], and total peripheral resistance (TPR) calculated as  $\text{MAP} / \text{Q}$ . Data were collected at a sampling frequency of 200 Hz and averaged over 5 successive beats. All parameters were extracted for the entire duration of baseline and bowel care, as well as for only the first 25 minutes of bowel care. Maximal responses were also determined during bowel care regardless of the time at which they occurred ( $\text{Parameter}_{\text{max}}$ ). AD was defined as an increase in  $\text{SAP}_{\text{max}}$  of at least  $20\text{mmHg}$  [29] compared to baseline. The overall burden of AD was determined from the area under the SAP curve (the product of SAP and heart beat).

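### Fisher's exact test treats lidocaine and placebo proportions as coming from 26 independent people, although both conditions are measured in the same 13; a paired binary test should replace it

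*Combined protocol and SAP*

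**What the plan says.** Under Experimental Procedure the trial is a "double-blind placebo-controlled crossover clinical trial where participants were randomised to a series of two treatments", and "seven participants were randomised to the lidocaine arm of the study first, and six to the placebo arm of the study first". All 13 people are therefore tested under both conditions.

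Under Statistical analyses, Fisher's "exact test was used to evaluate differences in proportions of responses between test conditions". No paired test for binary data is named there or elsewhere. In the same section, comparisons of cardiovascular outcomes and symptoms between conditions and test phases "were performed using two-way repeated measures ANOVA", so the pairing is respected for those outcomes.

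The plan does not list the proportions that were tested. The plausible case is in Data analyses: "AD was defined as an increase in" maximal systolic pressure of at least 20 mmHg over baseline, which is a yes/no result for each person under each condition.

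**The concern.** Fisher's exact test compares two independent groups. Here the two groups are the same people. The table of condition against response keeps only the two totals and discards which participants responded under one condition and not the other. That within-person change is the evidence a crossover is run to obtain.

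Two things are at stake. If a person's responses under the two conditions tend to agree, Fisher is too conservative, and a consistent shift in one direction can be reported as non-significant and read as no effect. If they tend to disagree strongly, Fisher can declare significance that a paired test does not support, and its type I error can exceed 5%.

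**Working it through.** **Inputs.** There are 7 + 6 = 13 people, hence 13 × 2 = 26 person-visits with complete data (Experimental Procedure). The significance threshold is 0.05 (Statistical analyses). The plan gives no observed or expected proportion and no within-person correlation, so those below are assumptions. It also states no figure for proportions that could be reproduced: its sample size of 13 concerns the systolic pressure difference.

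**Tests.** For each outcome let *a* = responders under both conditions, *b* = placebo only, *c* = lidocaine only, *d* = neither, with a + b + c + d = 13.

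- Fisher uses only the totals a + b and a + c, each out of 13.
- Exact McNemar: p = 2·P(X ≤ min(b, c)), X ~ Binomial(b + c, ½), capped at 1.
- Mid-p McNemar: the exact p minus P(X = min(b, c)).

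**Step 1: same totals, different evidence.** Take 10/13 on placebo and 4/13 on lidocaine.

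| b vs c | Fisher | Exact McNemar | Mid-p |
|---|---|---|---|
| 6 vs 0 | 0.047 | 2 × 1/64 = 0.031 | 0.031 − 1/64 = 0.016 |
| 7 vs 1 | 0.047 | 2 × 9/256 = 0.070 | 0.070 − 8/256 = 0.039 |
| 8 vs 2 | 0.047 | 2 × 56/1024 = 0.109 | 0.109 − 45/1024 = 0.065 |
| 9 vs 3 | 0.047 | 2 × 299/4096 = 0.146 | 0.146 − 220/4096 = 0.092 |

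**Step 2: a missed shift.** Take 9/13 versus 4/13 with all five changers moving the same way (5 vs 0). Fisher gives 0.115, exact McNemar 2 × 1/32 = 0.0625, and mid-p 0.0625 − 1/32 = 0.031.

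**Step 3: every possible table.** Four cells summing to 13 give C(16, 3) = 560 tables. Fisher and mid-p disagree at 0.05 in 28:

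- In 14, only mid-p is significant. All have 5 vs 0 discordant pairs, sample correlation (phi) +0.31 to +0.44, and Fisher p from 0.073 to 0.115.
- In 14, only Fisher is significant. These have phi from −0.43 to −1.0 and mid-p from 0.057 to 0.092.

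Against exact McNemar, Fisher alone is significant in 36 tables and exact McNemar alone in none. These are counts of tables, not probabilities.

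**Step 4: type I error.** Sum multinomial probabilities over the 560 tables, with P(both) = p₁p₂ + φ√[p₁(1 − p₁)p₂(1 − p₂)] and the other cells by subtraction. At an assumed common rate of 0.5:

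| φ | Fisher | Exact McNemar | Mid-p |
|---|---|---|---|
| −0.3 | 0.057 | 0.021 | 0.041 |
| 0 | 0.029 | 0.015 | 0.036 |
| 0.3 | 0.009 | 0.007 | 0.022 |
| 0.5 | 0.0025 | 0.0021 | 0.010 |

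Over rates 0.05 to 0.95 and feasible correlations from −0.9 to 0.95, in steps of 0.05, the mid-p maximum is 0.042 (rate 0.4, φ = −0.65). Fisher at that point is 0.085.

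**Step 5: power.** As an example of the cells, rates 0.8 vs 0.4 with φ = 0.3 give P(both) = 0.32 + 0.3 × √0.0384 = 0.379, then 0.421, 0.021 and 0.179.

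| Assumed rates | φ | Fisher | Exact McNemar | Mid-p |
|---|---|---|---|---|
| 0.8 vs 0.4 | −0.3 | 0.47 | 0.30 | 0.41 |
| 0.8 vs 0.4 | 0 | 0.46 | 0.35 | 0.48 |
| 0.8 vs 0.4 | 0.3 | 0.45 | 0.41 | 0.60 |
| 0.8 vs 0.5 | 0.3 | 0.22 | 0.18 | 0.33 |

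**The case against.** The strongest reply has four parts.

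- **The exact table is inferred.** The plan does not show how the table was built, and 26 is 13 × 2 rather than a stated figure. Since "Two participants chose not to complete the post-bowel care questionnaire", questionnaire items would have 13 − 2 = 11 complete pairs. A Fisher test of sequence against direction of change would be valid in a crossover. This stands in part: the wording points to a comparison between conditions and describes no such construction, but one sentence cannot rule it out. The figures above apply to outcomes with all 13 pairs.
- **The affected outcomes are secondary and unlisted.** This is true, and it limits the severity. It is also a reason to ask for the list.
- **Fisher errs mostly on the safe side.** This is correct for zero or positive correlation, which is what one would expect in people selected for a history of AD. But a test run at about 0.9% or 0.25% when 5% is intended is miscalibrated, and the price is missed effects.
- **Pairing alone does not rescue power.** This stands. Exact McNemar gains no table over Fisher and had less power in every case in Step 5. In the 5 vs 0 pattern it too misses 0.05. The power gain comes from mid-p, which has no theoretical guarantee of level, although it stayed at or below 0.042 on the grid checked. The choice of test would now also be made after unblinding, so its independence from the results cannot be verified.

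**Conclusion.** The concern holds. As written, the test for proportions assumes an independence that the crossover does not have. The main case for change is validity: the p-value should reflect who changed, and Fisher's cannot. In size, identical totals of 10/13 and 4/13 give one Fisher value, 0.047, where the paired mid-p value lies anywhere from 0.016 to 0.092. Under assumed positive correlation Fisher is conservative, and mid-p has more power (0.60 against 0.45 at rates 0.8 vs 0.4, correlation 0.3). At correlation −0.3 the order reverses (0.41 against 0.47).

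These results rest on 13 complete pairs and on assumed rates and correlations. The primary outcome and its sample size are not touched. No observed proportions are given, so it cannot be said whether any reported conclusion would change. This should be fixed, but it does not threaten the main result.

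**What to change.** In Statistical analyses:

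1. List each proportion compared between lidocaine and placebo, and say how its table was formed.
2. Replace Fisher's exact test for these comparisons with one paired binary test, chosen without regard to the results. Mid-p McNemar is the suggested default. Exact McNemar suits a preference for strict level control. A period-adjusted paired test using the 7/6 sequence groups is a third option.
3. For each comparison report the number of complete pairs, both discordant counts, and a paired risk difference with 95% CI. With the discordant counts in print, a reader can compute either McNemar p-value, which answers most of the worry about choosing a test after unblinding.
4. As a clarification of wording only, state that the t tests between conditions are paired.

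The cost is one sentence and a re-run of a few tests on data already held. R is already in use, and mid-p needs only binomial probabilities. Borderline p-values may move in either direction. Choosing exact McNemar would cost power relative to Fisher in the cases checked; choosing mid-p gives up a guaranteed level.

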### **Cardiac rate and rhythm analyses**

Electrocardiogram data were visually inspected offline after completion of the study. The number of beats that met criteria for bradycardia ( $<60\text{bpm}$ ) and tachycardia ( $>100\text{bpm}$ ) was determined during baseline and bowel care, and expressed as a percentage of the total number of beats in the corresponding phase. In addition, each beat was classified as either sinus rhythm, or not, and any arrhythmia or conduction abnormalities noted.

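### The blind is not shown to cover the statistical stage, where the test family, the primary systolic pressure summary and the secondary models were still open

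*Combined protocol and SAP*

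**What the plan says.** Two consecutive sentences close the Statistical analyses section of the combined protocol and SAP. The first is "Researchers, participants, care providers, and those analysing the data were blinded to the test condition". The second is "Researchers were unblinded just prior to statistical analyses".

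The same section assigns data processing to R and statistical testing to SigmaPlot, so the document treats these as separate stages. On choice of test it says: "Data were tested for normality and parametric or non-parametric assumptions were used as appropriate". It names no normality test and no threshold. Correlations and regressions are announced without saying which variables they relate.

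The primary outcome is in the Participants section: "Our primary outcome measure was the difference in systolic arterial pressure between the placebo and lidocaine conditions". No time window or summary measure is attached to it. The Data analyses section produces several candidates. Two of them are time windows: "All parameters were extracted for the entire duration of baseline and bowel care, as well as for only the first 25 minutes of bowel care". Another is a peak value: "Maximal responses were also determined during bowel care regardless of the time at which they occurred". The last is an area measure: "The overall burden of AD was determined from the area under the SAP curve".

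**The concern.** The first closing sentence tells the reader that analysts were blinded. The second places the unblinding of researchers before any test is run. Both can be true if analysing in the first sentence means signal processing, or if the person running the tests was not among the researchers unblinded. The document does not say which.

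This matters because of what was still undecided when the code was broken. Blinding the statistical stage adds little if the endpoint, test and models are already settled. Here they were not settled in the document, so labels may have been visible while those choices were made. The stake is credibility: a reader may credit the primary comparison with masked analysis when the text supports that only up to the end of signal processing.

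**Working it through.** No figure in the plan rests on the blinding statement, so there is none to reproduce. The check sets the sections side by side and then asks what the open choices could cost.

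**1. What the blind covers**

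| Step | Section | Position relative to unblinding |
|---|---|---|
| Home visits, recording, bowel care timing | Experimental Procedure | Before; covered |
| ECG reading and beat classification ("Electrocardiogram data were visually inspected offline after completion of the study") | Cardiac rate and rhythm analyses | Appears to be before; covered on the natural reading |
| Pressure extraction and derivation of the SAP summaries | Data analyses; R step in Statistical analyses | Appears to be before; covered on the natural reading |
| Normality check and choice of test family | Statistical analyses | Not shown to be covered |
| Which SAP summary carries the primary comparison | Participants and Data analyses (none fixed) | Not shown to be covered |
| Which correlations and regressions to run | Statistical analyses | Not shown to be covered |

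The document mentions no data lock, no rule fixing these choices before the code was broken, and no analysis under masked condition labels.

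**2. What the open choices could cost**

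Inputs: 13 participants and alpha 0.05 (Participants section). Assumptions, because the document does not give them: no true effect, normally distributed paired differences, equal correlation between SAP summaries, two-sided testing, and the paired t test and exact Wilcoxon test standing in for the parametric and non-parametric options.

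- If the summaries were independent, the chance of at least one p<0.05 using t tests alone is 1 − 0.95^k. For k = 3 it is 1 − 0.857 = 14.3%; for k = 4 it is 1 − 0.815 = 18.5%.
- With correlated summaries (20,000 simulated trials per setting), the chance of at least one p<0.05 is:

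| SAP summaries to choose from | Correlation 0.5 | 0.8 | 0.9 |
|---|---|---|---|
| Three, t test only | 12.4% | 10.2% | 8.5% |
| Three, t or Wilcoxon | 14.0% | 11.3% | 9.8% |
| Four, t test only | 16.1% | 11.6% | 9.6% |
| Four, t or Wilcoxon | 18.1% | 13.1% | 10.9% |

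- With one fixed summary and free choice between t and Wilcoxon, the rate is about 5.3–5.9%. The unfixed summary therefore matters much more than the test family.

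**3. Does seeing the labels change these rates?**

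A two-sided p-value is unchanged when the two condition labels are swapped. Someone choosing the smallest p under labels A and B therefore reaches the same rates. A direct check with three summaries at correlation 0.5, taking the smallest p from either test, gave a significant result favouring lidocaine in 7.1% of null trials whether labels were hidden or visible. That is half of an overall rate of about 14%, as symmetry requires. The table measures an unfixed endpoint, not the unblinding.

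**The case against.** The strongest reply is that this is a matter of wording.

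- Researchers and those analysing the data are listed as separate groups, and only researchers are said to have been unblinded. The person running SigmaPlot may have stayed masked. This stands, and it lowers confidence; but the document does not say so, and the reader cannot tell.
- The timing is disclosed in the very next sentence, and unblinding after processing is not itself a fault. This also stands. The weakness comes from combining it with choices not yet fixed.
- The choices may be less free than modelled. The test was to follow a normality check. Applying such a rule (Shapiro-Wilk at 0.05, an assumption because no test is named) gave 5.2–5.6%. Both time windows are produced, and the document does not say that one would be picked over the other. Cardiovascular outcomes are assigned to repeated measures ANOVA, and Wilcoxon is never named. These points confirm that the rates above are ceilings. They do not supply the missing primary summary.

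Two stronger readings are tempting. A reader might infer that the blind fails wherever judgement enters. The documents do not support that: ECG reading, beat classification and pressure extraction all need judgement and appear to precede unblinding. A reader might also take error rates of about 8–14%, the range for two or three summaries, as the price of the unblinding. They are not, for the reason in step 3 of the working. Nor does anything in the document show that selective choice occurred.

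**Conclusion.** The point holds in limited form, with moderate confidence. The two closing sentences need reconciling. As written, masking is supported for collection, ECG reading and signal processing, and is not shown for the statistical stage, where the test family, the primary SAP summary and the correlations and regressions remained open.

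The effect of the unblinding has no defensible number. Visible labels permit steering by direction of benefit, for example in how an unfavourable result is followed up or presented, but this cannot be quantified from the document. The separate exposure from an unfixed SAP summary has a ceiling of roughly 10–18% for three or four summaries with either test, at assumed correlations of 0.9 to 0.5. It falls only if the choices are fixed beforehand.

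The conclusion rests on reading data processing and statistical analysis as successive stages, and on there being no fixed rule recorded elsewhere. It bears on how the result should be interpreted and does not invalidate the trial.

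**What to change.** **If the code can still be withheld.** Name one SAP summary as primary and state the rule for choosing the test, including the normality test and threshold. List the planned correlations and regressions. Give the analyst the conditions coded A and B, with the same code for every participant; the ANOVA, t test and Fisher comparisons of conditions run identically on coded labels. Release the code only after the processed dataset, the choices and the outputs are finalised and dated. Fixing the choices is what limits selection; the coded labels add protection against steering by direction.

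**If the code was already broken**, which the past tense and the end of testing in October 2018 suggest: restate the blinding as covering collection and signal processing only. Say who was unblinded and when, and whether the person running the tests was among them. State anything that was fixed beforehand, if it was. Report every SAP summary (whole session, first 25 minutes, maximum and area under the curve).

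**Cost.** The first route needs wording and a later hand-over of the code. The researcher outside the team who drew the sequence could keep it, although the document does not say who held it. The second route needs wording and a fuller results table. The sample size of 13 does not change in either case.
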